Exclusion Criteria:

- Cases with primarily penetrating head trauma
- Pre-injury history of diagnosed ADHD (cases with questionable or selective features pre-injury may be considered as long as there is a clear worsening of symptoms)
- Pre-injury history of other neurodevelopmental disorders including intellectual disabilities, major communication disorders, or autism spectrum disorder
- Unstable or serious psychiatric conditions, such as psychotic symptoms. Concurrent problems with depression, anxiety, or posttraumatic stress disorder may be present but are judged to be stable and not so severe as to require pharmacologic treatment.
- Treatment with psychotropic medication(s), including stimulants, within the past 6 weeks, but eligible thereafter
- Lifetime history of stimulant abuse or dependence. Other (non-stimulant) substance abuse within the past 6 months
- Tics or other contraindications for psychostimulant use including cardiovascular disease, uncontrolled hypertension or hyperthyroidism, glaucoma, agitation, use of an MAO inhibitor within the past 6 weeks. Pregnancy would also be an exclusion for girls of childbearing age.
- Estimated IQ < 70
- Sensory and/or motor impairment(s) seriously limiting testing options
- Neurological conditions including uncontrolled epilepsy, degenerative disorders, brain tumor, or primary stroke
- Physical condition affecting arousal, activity level or stamina including uncontrolled thyroid dysfunction, severe or symptomatic anemia, autoimmune or metabolic disorders, untreated moderate/severe sleep apnea, etc.

Recruitment Plan:

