Next, potentially appropriate children and their parent(s) will be invited to come in person for a final determination of eligibility. Each will undergo a semi-structured interview by the project neuropsychologist/principal investigator ([name]) to obtain more detailed information about the TBI (including any pre- or post-traumatic amnesia, immediate cognitive or behavioral changes) and any persisting problems with attention and related areas, including symptoms of overactivity/impulsivity or underactivity (fatigue, diminished speed/stamina), the presence of any co-morbid psychiatric conditions (depression, anxiety, etc.), as well as clarification of premorbid history. In addition, questionnaires and rating forms will be used in eliciting detailed information on current cognitive and behavioral status. This will include behavior ratings on the Conners-3 Parent Form assessing ADHD and related areas. Selection will require a T-score of 65 or higher (+ 1.5 SD) on one or more of the following subscales: *Inattention*, *Hyperactivity/Impulsivity*, as well as *DSM-ADHD Inattentive Symptoms*, *DSM-ADHD Hyperactive-Impulsive Symptoms*. Parents will also complete a Post-TBI Symptom Questionnaire, which will further delve into mental functioning (children, ages 11 and older, will complete this as well). Subject selection will require that, categorically, attention problems be rated as among the most troubling cognitive symptoms persisting since the TBI. Each case will also be screened in terms of a having the necessary minimum IQ of 70. That will be estimated with the Vocabulary subtest of the Wechsler Intelligence Scale for Children-Fifth Edition (WISC-V), and will require a scaled score on it of 4 or higher.

Lastly, each candidate will undergo a brief physical exam and review of medical history by the project physician. Enrollment is contingent on verifying the absence of any contraindications for psychostimulant use as noted above. Female patients of child bearing potential also must have a negative urine pregnancy test in order to be enrolled. Parents will be provided with information to help them guide their daughters on avoiding pregnancy and what actions should be taken if they were to become pregnant while in the study.

Upon meeting all eligibility requirements, parents will go through an informed consent process concerning their child's participation in the study. Any forms and procedures used will be approved by the Vanderbilt IRB.

Study Design

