As in the initial study, this will be a randomized, double-blind, placebo-controlled, crossover trial. Following enrollment, each case will be randomly assigned to one of two treatment sequences, alternating on whether stimulant treatment or placebo comes first. Each phase will be 6 weeks long, resulting in a total duration of 12 weeks. Comprehensive neurobehavioral assessments will occur at baseline, 6 weeks, and 12 weeks. More streamlined behavior ratings along with safety monitoring and medication/placebo dispensing (see below) will be done during weekly visits.

Medication Trial

Source: Medication will be supplied by Shire Pharmaceuticals. The Vanderbilt Investigational Drug Service (IDS) will repackage the active medication to provide placebo and drug capsules identical in size (the smallest available) and appearance that will remain the same throughout the trial. The IDS will perform medication blinding and distribution to the study nurse.

Protocol: Enrolled children will enter a pre-determined randomization scheme as designed by the IDS. They will receive LDX (Vyvanse) 20-70 mg or placebo for 6 weeks. At the end of six weeks (day 43 after treatment initiation) each subject will switch from the current agent (drug or placebo) to the alternative (drug or placebo). Based on manufacturer's guidelines and clinical experience, no taper or washout period is deemed necessary either in switching from active drug to placebo or at termination of treatment.

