Safety Assessment: Patients will undergo weekly (+/-3 days) monitoring by the project nurse. Safety monitoring will include assessment of any self- or parent-reported adverse events (AEs), assessments of blood pressure, heart rate and weight, as well as psychiatric symptom assessment including suicidality.

Safety Endpoints: Safety endpoints will serve as withdrawal criteria if met or exceeded. They include:

Psychiatric

- New onset suicidality
- Mania
- Psychosis
- Other acute and serious reaction requiring immediate psychiatric intervention

Medical

- Hypertension (SBP and/or DBP greater than 95th percentile for child's age on two or more consecutive readings separated by at least 10 minutes)

- Tachycardia (symptomatic tachycardia or sustained heart rate greater than 150% of resting baseline heart rate on two or more consecutive readings separated by at least 10 minutes)
- Chest pain (judged by the study physician to be of likely cardiac origin)
- Other evidence suggestive of severe adverse effect of study drug
- Significant weight loss (> 10% compared to baseline level, and which persists despite downward titration)
- Pregnancy
- Introduction of a medication by subject's medical provider if that medication is on the list of excluded medications

Parents will be provided with contact information and instructions of what to do if questions or concerns regarding possible problems or safety issues should arise. Adverse medical events will be brought to the attention of the project physician who will initiate appropriate follow-up action as needed. All adverse events will also be communicated immediately to the PI (see below). Withdrawn patients and their parents will be provided with an explanation for their withdrawal and will be referred to an appropriate care provider for clinical management as needed.

Safety Reports: All adverse events (AEs) will be communicated immediately to the PI for follow-up review. Severe adverse events (SAEs) will be reported to the PI, IRB and study sponsor according to IRB guidelines.

The following are types of events that require reporting to the IRB. If the event does not fit the categories, the event is not reportable to the IRB; however, it may be reportable to the sponsor.

- a) Any event that requires prompt reporting to the sponsor, in accordance with the protocol (e.g., serious adverse events);
- b) Accidental or unintentional change to the IRB-approved protocol that involves risks or has the potential to recur;

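### No pregnancy test is scheduled after enrolment, so a girl randomised to placebo first takes her first LDX dose about six weeks after her only test

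*Combined protocol and SAP*

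**What the plan says.** Boys and girls aged 6 to 16 are eligible. The Exclusion Criteria state: "Pregnancy would also be an exclusion for girls of childbearing age". Screening Assessments/Enrollment adds the test requirement: "Female patients of child bearing potential also must have a negative urine pregnancy test in order to be enrolled". The same section provides for counselling: "Parents will be provided with information to help them guide their daughters on avoiding pregnancy and what actions should be taken" if a pregnancy occurs during the study.

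The trial is a two-period crossover with six weeks per period and no washout. Under Medication Trial, Protocol: "At the end of six weeks (day 43 after treatment initiation) each subject will switch from the current agent (drug or placebo) to the alternative". Study Design says of the visits in between: "More streamlined behavior ratings along with safety monitoring and medication/placebo dispensing (see below) will be done during weekly visits".

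Under Safety Monitoring, Safety Assessment: "Patients will undergo weekly (+/-3 days) monitoring by the project nurse", and "Safety monitoring will include assessment of any self- or parent-reported adverse events (AEs), assessments of blood pressure, heart rate and weight", followed by a psychiatric symptom check. Pregnancy is on the medical list under Safety Endpoints, where the rule is: "Safety endpoints will serve as withdrawal criteria if met or exceeded". The 6- and 12-week batteries under Neurobehavioral Assessments consist of cognitive tests and rating scales only.

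**The concern.** The plan has already decided that a pregnant girl should not be dosed: she may not enter, and she must leave if she becomes pregnant. The enrolment test enforces that decision just before first LDX exposure in one sequence only. In the other, six weeks on placebo pass between the test and the first LDX dose, and randomisation alone decides which applies.

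After enrolment, detection depends on the girl or her parent reporting a pregnancy at a weekly nurse visit. If she conceives during the placebo phase and does not know, or does not say, the schedule starts her on 20 mg and, if tolerated, moves her to 30, 50 and 70 mg over the next three weeks.

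Most other safety endpoints are paired with a planned check. Blood pressure, heart rate and weight are measured weekly, psychiatric symptoms are assessed weekly, and new medications are asked about specifically. Pregnancy has no named measurement or specific inquiry after entry, although a simple test for it is already in the plan.

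**Working it through.** The check is calendar arithmetic plus a read of the whole document for any later test.

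**Inputs**
- Tests described: one, at enrolment (Screening Assessments/Enrollment).
- Phase length: 6 weeks, 12 weeks in total (Study Design).
- Switch: day 43, no washout (Medication Trial, Protocol).
- Visit window: ±3 days for weekly monitoring and for the 6- and 12-week assessments.
- Days from the test to study day 1: not given; call this *s*. For illustration I assume 0 to 14 days.
- Sample: approximately 20 children (Subject Selection). The number who are girls of childbearing potential is not given; call this *g*.

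**The plan's own figure.** 6 × 7 = 42 days of first-phase treatment, so the second phase begins on day 43, as stated.

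**Age of the only test at the first LDX dose**
- LDX first: *s* days, or 0 to 14 under the assumption.
- Placebo first: (43 − 1) + *s* = 42 + *s* days, or 42 to 56 under the assumption.
- If the switch moves with a visit held 3 days early or late (days 40 to 46), the placebo-first figure runs from 39 + *s* to 45 + *s* days. The protocol fixes the switch at day 43, so this range is itself an assumption.

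**Age of the test at the end of treatment.** Two six-week phases end on day 84, so a placebo-first girl finishes LDX (84 − 1) + *s* = 83 + *s* days after her only test.

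**With a re-test at the week-6 visit, before the switch**
- Same-day switch: 0 days.
- Visit window centred on day 43, visit on day 40, switch on day 43: 3 days.
- Visit window centred on day 42, visit on day 39, switch on day 43: 4 days.

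**How many girls.** Assuming equal allocation to the two sequences, about *g*/2 are placebo first. The arithmetic limits are *g* = 0 (none) and *g* = 20 (about 10). The upper limit would require every child enrolled to be a girl of childbearing potential, so it is a bound and not an expectation. The document gives no basis for a conception rate over six weeks, and I have not estimated one.

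**The case against.** The best case against has four parts.

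- **The list may be incomplete.** The document is a short proposal, the weekly safety list is not said to be exhaustive, and the parent materials are not shown. A re-test may be intended. That is fair, but a test that is not written down is not scheduled; if one is intended, a single line settles the matter.
- **Safeguards already exist.** There is an exclusion, an entry test, guidance to parents, weekly nurse contact and a withdrawal rule. These narrow the gap to a pregnancy that is unrecognised or not disclosed. They do not close it, because every safeguard after entry depends on someone knowing and saying so.
- **The asymmetry is in the age of the test, not in all exposure risk.** A girl on LDX first who conceives during weeks 1 to 6 can also be exposed without detection, and a week-6 test does nothing to shorten that. This stands. The proposed change protects the start of LDX, not the six weeks that follow.
- **The size is small or unknown.** The number affected could be zero, and the documents do not allow the degree of harm to be sized. This also stands, and it limits the weight of the point. The testing cost shrinks with the same number.

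**Conclusion.** The concern holds. The document describes one pregnancy test, at entry, and a girl in the placebo-first sequence starts LDX 42 days plus the screening delay after it. That is about six weeks at the least if the switch is on day 43 as written, and 42 to 56 days if the delay is 0 to 14 days. Followed as written, the plan could start LDX in a girl whose pregnancy is unrecognised or undisclosed, contrary to its own exclusion and withdrawal rules.

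The conclusion rests on the text supplied, in which no later test appears. It does not rest on any estimate of conception or fetal risk. It has no bearing on the efficacy analysis. The change should be made because it is cheap and improves participant safety; confidence in its practical weight is moderate, since the number of girls concerned is unknown and may be nil.

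**What to change.** Add to Safety Monitoring, Safety Assessment: girls of childbearing potential repeat the urine pregnancy test at the week-6 visit, and second-phase capsules are dispensed only after a negative result. Apply this in both sequences, so that having the test does not reveal the order. A positive result invokes the existing withdrawal endpoint. A test at week 12 or on early exit is optional; for placebo-first girls it could only find a pregnancy after exposure.

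The cost is one protocol line, one consent and assent sentence, and *g* extra urine tests (0 to about 20) at a visit already scheduled, with no new visit or staff. The amendment needs IRB approval, and the site should settle beforehand how a positive result in a minor is handled and who is told. The downsides are a small burden on the adolescents concerned and, for girls who had LDX first, a test that serves mainly to protect the blind. Undetected exposure arising within an LDX phase would remain possible.

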This study will follow a design and methodology similar to what was done in the initial study, albeit adapted to the age range of the child sample. There will be some differences, however. The proposed study will not incorporate fMRI methods as was done in the initial trial. Instead, the focus will be on examining clinical outcomes based strictly on a broad range of standardized cognitive and neurobehavioral measures. That is intended not only to streamline the cost of the proposed study; it also will allow subject selection to be less restrictive. A number of otherwise suitable cases had to be excluded in the previous trial due to failing to meet criteria specifically having to do with the MRI scanning (e.g., no metal objects or implanted devices, claustrophobia, etc.). More generally, it was felt that there would be fewer potential problems with the participation or compliance of children if fMRI scans were not involved.

Also, unlike the initial trial, subject selection will not be restricted to only those with moderate-severe TBI. It will be extended to also include cases with milder TBI who have documented persistence in cognitive changes, including impaired attention. That would encompass many common cases of TBI, and greatly broaden the potential pool. Even if the attention deficits in these cases would not prove to be chronic, helping to enhance functioning in the earlier stages of recovery can have a beneficial effect on overall outcomes and limit secondary problems that might otherwise arise. Lastly, the interval from the time of injury to when a case is eligible for inclusion in the study will be reduced from 6 months to 2 months. This is intended to capture the child subjects earlier on in the recovery process. It will help reduce the attrition of potential cases who otherwise might be lost to follow-up or who wind up getting started on other treatments. Regardless of the exact point within the eligible time interval post-injury, it will be necessary that each case be judged to be neurologically stable but having persistent attention deficits.

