This will be the first study to examine the use of LDX in treating attention deficits in children with TBI. It will be the most rigorous study to date examining stimulant medication treatment of any kind with this population. It is predicted that, as in the initial trial with adults, positive treatment effects will be found on a spectrum of outcomes having to do with attention and the various areas affected by it. Safety and tolerability will be carefully examined for the use of LDX in this clinical application. Also, as was done in the initial trial, treatment outcomes will be examined in terms of potentially moderating effects having to do with a broad range of pre-treatment subject characteristics and injury variables, including the pattern and severity of TBI, age of injury, as well as certain cognitive and behavioral factors at baseline. In our previous trial with adults, subjects with greater functional limitations pretreatment (lower IQ, problems with executive functioning) showed better treatment response with LDX on some outcome indices.

Overall, this will be a novel study examining the treatment of TBI-related attention deficits in children. The primary aim is to conduct a sound clinical trial examining outcomes with LDX as the treatment, but the objectives of the study go beyond that. More broadly, the aim is to gain further insights into the nature of attention deficits and their treatment in children with TBI. Based on the existing research, there are likely to be unique relationships involving children with TBI versus idiopathic ADHD. The hope is that this trial will help inform and guide further investigations in this area.

Methods

Subject Selection

The subject sample is to consist of approximately 20 children diagnosed with TBI-related attention deficits. The specific selection criteria are noted below.

Inclusion Criteria:

- Males and females ages 6 to 16
- Traumatic brain injury rated as mild/moderate/severe (based on *Glasgow Coma Scale*, estimated posttraumatic amnesia, indications of intracranial injury on CT scan, etc.)
- Sustained 2-36 months earlier
- Considered to be neurologically stable (absence of post-acute symptoms of confusion, disorientation, etc.)
- Persistent (> 2 months) problems with focused or sustained attention
- Problems with attention/concentration rated as among the most prominent cognitive changes
- Accompanying features may include diminished arousal/speed/stamina and/or hyperactivity/impulsivity symptoms.

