After completion of the full trial, individual participants will be provided information from the IDS indicating the particular order of treatment in their case. This will allow them and their parents the option of sharing their subjective experiences with their primary care provider, including any perceived benefits from Vyvanse, in consideration of possibly pursuing further treatment on their own. However, the blinding of project staff with respect to treatment order will be maintained for all cases throughout the study until after the follow-up interview (see below) is completed on the final study subject.

Post-study follow-up: Parents (and subjects 11 years and older) will be contacted by phone 2-weeks (+/-3 days) after the final study day to inquire about safety and to address any questions or concerns they may have.

Note. Concomitant medications not listed in the exclusion criteria will be permitted. No medications will be changed or held for the purposes of entering the research study. If a child is started on a new medication by their medical provider, and that medication is on the list of excluded medications, the patient will exit the study. Inquiry as to possible medication changes/additions will be specifically assessed as part of the monitoring of safety and compliance in weekly visits with the study nurse.

Neurobehavioral Assessments

All cases will receive a one-time assessment at baseline on the following measures. These will be used as covariates or component measures facilitating interpretation on other tests.

- Abbreviated Wechsler Intelligence Scale for Children- Fifth Edition (WISC-IV; general intelligence)
- Wisconsin Cart Sorting Test (set maintenance/shifting; executive functioning)
- Finger Oscillation (fine-motor speed/persistence)

The following are repeatable measures that will be administered at baseline, 6 weeks (+/-3 days), and 12 weeks (+/-3 days):

- Conner's Continuous Performance Test (sustained attention, delay, response modulation)
- Stroop Color-Word Test- Children's Version (set maintenance/shifting; regulation of competing response tendencies)
- Letter & Animal Word Fluency, WISC-V Coding (processing speed/mental control)
- Woodcock-Johnson Understanding Directions (listening comprehension, following spoken instructions)
- WISC- V Digit Span (working memory)
- Wide Range Assessment of Memory and Learning-2: Verbal Learning and Design Memory subtests (short-term auditory-verbal memory and visual memory)

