Cases will also be distinguished based on whether there are indications of white matter injury evident on CT. Cases with/without CT indications of frontal lobe injury will be differentiated as well. These determinations, as well as the final severity ratings, will be made with the input of a physician with a specialty in the diagnosis and management of TBI in children.

Data Analyses

The double blind, crossover design allows for the assessment of both within-subjects and between subjects contrasts. The primary analyses will consist of multiple paired-samples t-tests comparing LDX versus placebo on each of the neurobehavioral dependent measures in the study.

No formal correction for multiple comparisons will be applied so as to not limit sensitivity in detecting possible treatment effects. A p value equal to, or less than, 0.05 will be considered statistically significant. All tests will be two-tailed. All analyses will be performed using Statistical Programs for the Social Sciences (SPSS for Windows, Version 21.0, IBM Corp, 2012).

Possible order effects (depending on whether drug treatment comes before or after placebo) will be examined through a separate analysis of variance (ANOVA) for each dependent measure using a two-factor model (treatment, order, and treatment x order interaction).

There will also be applications of analysis of covariance (ANCOVA) to determine possible mediating or moderating effects of certain pre-treatment variables on treatment outcomes (demographics, brain injury variables, IQ and other cognitive factors, motor control integrity, behavioral symptom profiles and personality features). We anticipate that the distribution of cases in terms of TBI severity will permit an analysis of comparative treatment outcomes for children with mild versus moderate versus severe brain injuries.

Also, safety data will be examined carefully based on weekly visits over the course of the trial. Comparisons will be made on LDX versus placebo for indices such as blood pressure and heart rate, side effects (insomnia, decreased appetite or weight loss, etc.) or significant adverse events, if any.

Safety Monitoring

Because this is a clinical trial of an FDA-approved medication with a favorable safety profile, there will be no independent data safety monitoring board (DSMB) or Safety Officer for this study. Patient safety will be monitored using best practice clinical care standards.

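### The primary paired t-test has no period term, so practice and recovery between weeks 6 and 12 inflate the error variance, or bias the LDX effect if sequences are unequal

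*Combined protocol and SAP*

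**What the plan says.** The Study Design section describes a two-sequence, two-period crossover with six weeks per period. The Data Analyses section then sets the primary analysis: "The primary analyses will consist of multiple paired-samples t-tests comparing LDX versus placebo on each of the neurobehavioral dependent measures in the study". On significance it says "A p value equal to, or less than, 0.05 will be considered statistically significant" and "All tests will be two-tailed".

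Order is handled separately: "Possible order effects (depending on whether drug treatment comes before or after placebo) will be examined through a separate analysis of variance (ANOVA", fitted for each measure "using a two-factor model (treatment, order, and treatment x order interaction". The plan does not say that the treatment test from this ANOVA replaces the t-test, and it gives no rule for what follows if an order effect appears. Period is not named as a model term.

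Three other statements bear on the point:

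- Neurobehavioral Assessments, on the outcome battery: "The following are repeatable measures that will be administered at baseline, 6 weeks (+/-3 days), and 12 weeks (+/-3 days". Alternate forms are not mentioned.
- Introduction, on shortening the minimum time since injury to two months: "This is intended to capture the child subjects earlier on in the recovery process".
- Subject Selection: "The subject sample is to consist of approximately 20 children diagnosed with TBI-related attention deficits". The Medication Trial section leaves the randomization scheme to the Investigational Drug Service and states neither an allocation ratio nor blocking.

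**The concern.** Two features of this trial make a change between week 6 and week 12 likely whatever the child is taking. The cognitive tests (verbal learning, design memory, coding, fluency, Stroop, continuous performance) are repeated, and some children are still recovering. A paired t-test on LDX minus placebo cannot separate that change from the drug effect within a child. It relies on the two sequences cancelling.

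If they cancel exactly, the shift still spreads the two sequences apart and is counted as random error. If they do not cancel, part of the shift is reported as drug effect. With about 20 children, either outcome matters.

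The labelling adds a risk. In a two-period, two-sequence crossover, the treatment-by-order interaction is the period effect. Ordinary practice gains would appear in that term, and a reader could take them to mean that the drug works only in one order.

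**Working it through.** The plan states no power, effect size, standard deviation or period effect, so there is no figure of its own to reproduce.

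**Inputs from the documents.** N of about 20; two-sided test at 0.05; two sequences, two periods; primary test without a period term.

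**Assumptions.** Let D be LDX minus placebo for one child, scored so that higher is better. Let s be the SD of D within a sequence, and P the average improvement from period 1 to period 2 unrelated to drug. P runs from 0 to 1.0 s. The true effect τ is 0.66 s, which gives the paired t-test about 80% power at N = 20 when P = 0. There is no carryover.

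**Step 1. Where the shift goes.** Mean of D is τ − P in LDX-first children and τ + P in placebo-first children.

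**Step 2. Paired t-test.** With n_L LDX-first and n_P placebo-first children:

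- Bias = P × (n_P − n_L)/N. For 12/8 (LDX-first/placebo-first) and P = 0.5 s: 0.5 × (8 − 12)/20 = −0.10 s, so the expected estimate is 0.56 s. For 7/13: 0.5 × 6/20 = +0.15 s, giving 0.81 s. For 7/13 and P = 1.0 s: +0.30 s, giving 0.96 s.
- Expected variance of D = s² + 4P² n_L n_P/[N(N − 1)]. For 10/10 and P = 0.5 s: 1 + 4 × 0.25 × 100/380 = 1.26 s². For P = 1.0 s: 1 + 400/380 = 2.05 s².

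**Step 3. Period-adjusted test.** Average the two sequence means of D. P cancels for any split. SE = (s_pooled/2) × √(1/n_L + 1/n_P), on N − 2 df. With s = 1 the SE is 0.224 for 10/10, 0.228 for 12/8 and 0.234 for 7/13.

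**Step 4. Operating characteristics.** Simulated with normal errors, 400,000 trials per cell. Splits are LDX-first/placebo-first.

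| Split | P (in s) | Mean paired estimate (true 0.66) | Paired power | Adjusted power | Paired type I error |
|---|---|---|---|---|---|
| 10/10 | 0.25 | 0.66 | 78% | 80% | 4.4% |
| 10/10 | 0.5 | 0.66 | 72% | 80% | 2.9% |
| 10/10 | 1.0 | 0.66 | 49% | 80% | 0.6% |
| 12/8 | 0.5 | 0.56 | 57% | 78% | 4.5% |
| 12/8 | 1.0 | 0.46 | 21% | 78% | 3.0% |
| 8/12 | 0.5 | 0.76 | 85% | 78% | 4.5% |
| 8/12 | 1.0 | 0.86 | 80% | 78% | 3.0% |
| 7/13 | 0.5 | 0.81 | 89% | 76% | 6.5% |
| 7/13 | 1.0 | 0.96 | 90% | 76% | 7.5% |

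The adjusted test is unbiased with 5% type I error in every cell. Where the paired test has the higher power (8/12 and 7/13), the gain comes from upward bias.

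**Step 5. How likely is imbalance?** If randomization were simple (an assumption), the binomial probability of an 8/12 split or worse, in either direction, is 0.50, and of 7/13 or worse 0.26. Averaged over such splits the paired estimate is unbiased and type I error is about 5%, but power is 71% against 77% adjusted at P = 0.5 s, and 50% against 77% at P = 1.0 s.

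**Step 6. What the planned ANOVA estimates.** In one test data set, the two-factor model was fitted as repeated measures with order between subjects. Its treatment t was 2.83, identical to the period-adjusted crossover t. Its treatment-by-order t (−4.60) was identical to the period t. The paired t was 2.67.

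**The case against.** The strongest reply is that the plan already contains the remedy. The order ANOVA, run for every measure, yields the period-adjusted treatment test if it is fitted as repeated measures with equally weighted sequence means. That is true, so it would be wrong to say the plan as a whole overlooks order. But the ANOVA is described as a check for order effects, has no decision rule, and leaves the unadjusted t-test as the headline result.

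Other points stand as limits on size:

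- No document gives a value for P. A shift of 1.0 s is the top of an assumed range; at 0.25 s with equal sequences the loss is only about two points of power.
- Eligibility runs to 36 months after injury and requires neurological stability. A baseline testing precedes both periods, so some practice gain is already spent. Much of the battery is parent or self-report, where test practice is a less obvious mechanism.
- What is inflated is the error variance, not generally the false-positive rate. Of the splits tabulated, type I error exceeds 5% only at 7/13.
- The bias depends on the realized split and averages to zero over randomization. A given trial has only one split, however, and the withdrawals that the protocol foresees can unbalance it further.
- A period term removes only the shift common to all children. Recovery that differs between children stays in the error.

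The trial also calls itself a pilot. That lowers the stakes but gives no reason to prefer the unadjusted test.

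**Conclusion.** The concern holds. The primary test omits period in a design where a period shift is plausible. With equal sequences the cost is lost power: from 80% to 72% at P = 0.5 s and to 49% at P = 1.0 s. With unequal sequences the estimate is also biased, by 0.10 s at 12/8 or 8/12 and 0.15 s at 7/13 when P = 0.5 s, and by twice that when P = 1.0 s. The algebra is exact for a common additive shift. The magnitudes rest on the assumed P, on τ = 0.66 s and on normal errors. The change should be made: the harm is conditional, but the correction is nearly free.

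**What to change.** In the Data Analyses section, make the period-adjusted LDX-placebo difference the primary result for every measure. Either of two analyses will do:

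- a mixed model with treatment, period and sequence as fixed effects and child as random effect; or
- a two-sample t-test comparing the within-child period differences between sequences, with the contrast halved to give the treatment effect.

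The two agree when every child completes both periods. Since withdrawals are foreseen, name one of them in advance.

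State that the treatment-by-order interaction is the period effect, and that the order term will not be used to decide whether data are kept. Retain the paired t-test as a sensitivity check. It would also help to state 1:1 blocked allocation to sequence.

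The cost is a change of wording; the SPSS package already named can fit either analysis. If there is no period effect, the adjustment spends one degree of freedom: power stays within half a percentage point of 80% at 10/10, and is about 78% at 12/8 and 76% at 7/13.
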